5.1. Determination of Sample Size

A total of approximately 290 patients (145 per group) will be randomized to have approximately 246 completers (123 per group) to show dulaglutide add-on titrated insulin glargine is superior to placebo add-on titrated insulin glargine with 90% power assuming a treatment difference of 0.5% in HbA1c reduction, standard deviation (SD)=1.2%, and dropout rate of 15%, and 2-sided alpha of 0.05. The screen failure rate is estimated as 40%. Approximately 483 patients will be screened.

5.2. General Considerations

This plan describes all priori statistical analyses for efficacy and safety that will be performed.

Statistical analysis of this study will be the responsibility of Eli Lilly and Company (Lilly), although implementation of the statistical analysis may be delegated to a third party. Any change to the data analysis methods described in the protocol will require an amendment ONLY if it changes a principal feature of the protocol. Any other change to the data analysis methods described in the protocol, and the justification for making the change, will be described in this SAP and/or in the clinical study report (CSR). Additional exploratory analyses of the data will be conducted, as deemed appropriate.

All analyses will be implemented using Version 9.4 SAS or higher.

Unless otherwise specified, listings will include all randomized patients. Both efficacy and safety analyses will be conducted using the intent-to-treat (ITT) population. Unless otherwise specified, efficacy data from patients who started rescue therapy or premature treatment discontinuation (whichever occurs first) will be censored from the point of initiating rescue treatments or early discontinuation onwards. Safety analysis will not censor this part of data. Selected analyses will also be conducted using the per-protocol (PP) and Completers populations. The PP and Completers populations are subsets of the ITT population.

Unless otherwise noted, all tests of treatment effects will be conducted at a 2-sided alpha level of 0.05, and confidence intervals (CIs) will be calculated at 95%, 2-sided. All tests of interactions between treatment groups and other factors will be conducted at a 2-sided alpha level of 0.10.

The baseline data will be collected at Visit 3. For all variables, including HbA1c, if baseline data are missing, the last non-missing measurement taken prior to this visit will be used for the baseline measurement.

Patients will be randomized in a 1:1 ratio to (1) dulaglutide 1.5 mg QW add-on to insulin glargine or (2) placebo QW add-on to insulin glargine, with metformin and/or acarbose. Patients will also be stratified by HbA1c at Visit 1 (screening) (<8.5% vs. \geq 8.5%) and OAM usage (metformin alone, acarbose alone, metformin and acarbose) at Visit 3 (randomization) to achieve

between-group comparability and to mitigate against confounding the effects of the treatments with severity of disease or treatment with metformin and/or acarbose.

The primary analysis model will be mixed-model for repeated measures (MMRM) analysis using restricted maximum likelihood (REML) with treatment, OAM usage (metformin alone, acarbose alone, metformin and acarbose), visit, and treatment-by-visit interaction as fixed effects, baseline HbA1c as a covariate, and patient as a random effect. An unstructured covariance structure will be used to model the within-patient variability and implicitly adjust for missing data. There will be no imputation of missing data for patients who have no postbaseline data.

If this analysis fails to converge, the following covariance structures will be tested in order:

- Toeplitz with heterogeneity
- Autoregressive with heterogeneity, by visit
- Compound symmetry with heterogeneous variances, by visit
- Toeplitz
- Autoregressive
- Compound symmetry without heterogeneous variances, by visit

The first covariance structure that converges will be used. The Kenward-Roger approximation will be used to estimate denominator degrees of freedom. Significance tests will be based on least-squares (LS) means using Type III hypotheses.

The percentage of patients achieving the target HbA1c of <7.0% will be analyzed using a longitudinal logistic regression with repeated measurements.

For continuous measures, summary statistics will include sample size (n), mean, SD, median, minimum (min), and maximum (max) for both the actual and the change from baseline measurements. Least-squares mean (LS Mean) and standard errors (SEs) derived from the model will also be displayed for the change from baseline measurements. Treatment comparisons will be displayed showing the treatment difference LS Mean and the 95% CIs for the treatment differences along with the p-values for the treatment comparisons.

For categorical measures, summary statistics will include sample size, frequency, and percentages. Fisher's exact test will be used.

5.3. Graphical Testing Scheme

To control type I error, a graphical testing scheme (Bretz et al. 2011) presented in **Error! Reference source not found.** will be used to compare treatments regarding selected secondary objectives once the primary objective has been achieved. The numbers in **Error! Reference source not found.** represent the fraction of alpha to allocate to the next hypothesis if the current null hypothesis is rejected.

[figure not shown]

Figure 5.1 Graphical testing scheme for H9X-MC-GBGO.

Note:

HbA1c: primary objective, superiority test of the addition of dulaglutide 1.5 mg QW vs the addition of once weekly placebo to insulin glargine on HbA1c change from baseline at Week 28.

Weight: superiority test of the addition of dulaglutide 1.5 mg QW vs the addition of once weekly placebo to insulin glargine on body weight change from baseline at Week 28.

Target: superiority test of the addition of dulaglutide 1.5 mg QW vs the addition of once weekly placebo to insulin glargine on HbA1c target 7.0% at Week 28.

FSG-NI: noninferiority test of the addition of dulaglutide 1.5 mg QW vs the addition of once weekly placebo to insulin glargine on FSG change from baseline at Week 28. Noninferiority margin of 12mg/dL (equivalent to 0.4% of HbA1c margin) will be used.

FSG-SP: superiority test of the addition of dulaglutide 1.5 mg QW vs the addition of once weekly placebo to insulin glargine on FSG change from baseline at Week 28.

5.4. Patient Population

The following patient populations described in [Table 5.1](#) will be used to analyze the data. The data collected in this study will be presented as listings including investigator site, patient, and treatment.

Table 5.1 Analysis Populations for Study H9X-MC-GBGO

Population	Definition
Entered	All patients who sign informed consent forms
Randomized	All patients who are randomized to a treatment arm
Nonrandomized	All patients entered, but not randomized to a treatment arm
Intent-to-Treat (ITT)	All patients randomized who take ≥ 1 dose of study medication for assigned treatment arm
Completers	All patients in the ITT population who complete the planned treatment period (that is, do not discontinue from the treatment early). Data after initiation of rescue therapy will be censored from the efficacy analyses. 
 • Note: There is no requirement that completers have to be on study drug the entire study.
Per-Protocol (PP, see details in the document Trial Issue Management Plan)	All patients in the ITT population who also meet the following criteria: 
 • Have no important protocol deviation expected to impact the primary endpoint for HbA1c (see below, Section 5.5.3); • Complete the planned treatment period (28 weeks [Visit 17]) for primary endpoint (that is, do not discontinue from the study drug early).

5.5. Treatment Group Comparability

5.5.1. Patient Disposition

A listing of patient discontinuation will be presented for all randomized patients. Frequency counts and percentages of all patients entered, randomized/enrolled, completing and discontinuing from the study and study treatment will be presented for both the treatment groups. A summary of discontinuations will also be presented by visit. The overall percent discontinued comparisons among the treatments will be performed using Fisher's exact test.

5.5.2. Patient Characteristics

Demographic and baseline clinical characteristics will be summarized by treatment group using ITT, PP and Completer populations. For continuous measures, summary statistics will include sample size (n), mean, SD, median, min, and max. Treatment differences will be analyzed using ANOVA model with treatment as the factor. For categorical measures, summary statistics will include sample size, frequency and percent. Treatment difference will be compared using Fisher's exact test.

5.5.3. Protocol Deviations

Important protocol deviations will be listed for all randomized patients. The rationale for choosing the important protocol deviations was based on their potential to impact the primary analysis.

A separate document (known as the Trial Issue Management Plan) will be used to define the categories, subcategories and study-specific term of important protocol deviations.

The listing of important protocol deviations (IPD) for all randomized patients during the entire study, with the indication of whether to be excluded from the PP population, will also be provided. The IPDs identified by site monitoring and clinical database will be integrated in the listing.

5.5.4. Concomitant Medications

Concomitant medications, including previous therapy for diabetes, will be summarized by treatment. Proportion of certain categories of concomitant medications will be analyzed using a Fisher's exact test.

5.5.5. Study Drug Compliance

Study drug compliance will be listed and summarized using ITT population. Study drug compliance is defined as taking at least 75% of the scheduled injections of the study drug between the visits of randomization (Visit 3, Week 0) and Week 4, 8, 12, 18, 24 and 28. The frequency and percent of patients who are compliant by treatment group will be summarized and compared using Fisher's exact test at these visits.

In addition, the overall compliance during the study will be calculated for each patient. The overall compliance in percentage for each patient will be calculated by taking the number of visits the patient was compliant divided by the total number of visits with non-missing compliance data for this patient *100. The overall compliance will be summarized and presented in descriptive statistics that include the sample size (n), mean, SD, median, min, and max. Overall treatment compliance for each patient is defined as taking at least 75% of the injectable study drug for at least 75% of the visits, that is, the overall compliance percentage is at least 75% for this patient.

5.5.6. Treatment Exposure

Treatment exposure is defined as the time from when a patient is randomized at Visit 3 and receives study drug until the patient either discontinues treatment or completes the treatment period.

The duration of treatment exposure will be summarized and listed by treatment group using ITT, PP, and Completer population. Duration of exposure will be categorized into the following groups: ≤ 14 days, > 14 to ≤ 28 days, > 28 to ≤ 56 days, > 56 to ≤ 84 days, > 84 to ≤ 126 days, > 126 to ≤ 196 days and > 196 days. These categories will be summarized as frequency counts by treatment group. Summary statistics will include mean per patient exposure in days, median, min, max and SD. The duration of treatment exposure will be analyzed using one-way ANOVA with treatment as fixed effects.

5.6. Primary Efficacy Analysis

The primary efficacy measurement in this study is change in HbA1c from baseline to Week 28, as determined by the central laboratory.

The primary analysis model will be MMRM for HbA1c change from baseline to Week 28 (Visit 17). The model will include treatment, OAM use, visit, treatment-by-visit interaction as fixed effects, and baseline HbA1c as a covariate and patient as a random effect. LS Mean, 95% CI and the p-value will be presented for the treatment difference (dulaglutide 1.5 mg minus placebo).

Primary analysis will be done using ITT population.

The MMRM analysis model for the primary endpoint will be repeated using the PP and Completer populations to check the sensitivity of the primary analysis.

5.7. Key Secondary Efficacy Analysis (Controlled for Type I Error)

5.7.1. Percentage of Patients Achieving a Target HbA1c <7.0%

Frequency counts and percentage of patients achieving the target of HbA1c <7.0% will be presented for the ITT population. The percentage of patients achieving the target of HbA1c <7.0% will be analyzed using longitudinal logistic regression with repeated measurements. The model will include independent variables of treatment, OAM usage, visit, and treatment-by-visit interaction as fixed effects and baseline HbA1c as a covariate.

5.7.2. Analysis of Body Weight and Fasting Serum Glucose (FSG)

Actual and change of weight and FSG from baseline will be summarized for the ITT population. The evaluation of the two dependent variables – change in body weight from baseline, and change in FSG from baseline, will be performed using MMRM model separately. The MMRM model will include treatment, OAM usage, visit, baseline HbA1c strata (<8.5%, and $\geq 8.5\%$), treatment-by-visit interaction as fixed effects, and baseline dependent variable as a covariate and patient as a random effect. LS Mean, 95% CI, and the p-value will be presented for the treatment comparison.

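### Randomisation is stratified on screening (Visit 1) HbA1c, but no efficacy model includes that stratum; the effect on inference is negligible and the correction is close to free

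*SAP*

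**What the plan says.** **Randomisation.** SAP 5.2 states "Patients will also be stratified by HbA1c at Visit 1 (screening", cut at 8.5%, with OAM usage as the second factor. Protocol 7.2 says the same.

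**Baseline.** SAP 5.2 and protocol 10.3.1 both define baseline as Visit 3. An earlier value is used only if Visit 3 is missing.

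**HbA1c term in each model:**

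| Analysis (SAP section) | HbA1c term | Visit 1 stratum |
|---|---|---|
| Primary HbA1c MMRM (5.6) | baseline HbA1c as covariate | no |
| HbA1c <7.0% and ≤6.5% (5.7.1, 5.8.1) | baseline HbA1c as covariate | no |
| Composite responders (5.8.1, 5.9.2) | baseline HbA1c, listed among the factors | no |
| Time to rescue, Cox (5.11.3) | baseline HbA1c as covariate | no |
| Weight and FSG (5.7.2; uncensored versions in 5.10) | baseline strata only | no |
| Self-monitored glucose, insulin dose, titration measures (5.8.2, 5.8.3, 5.9.1) | baseline strata only | no |
| Hypoglycaemia rates, vital signs, patient-reported outcomes (5.11.2, 5.11.4, 5.13) | baseline strata only | no |

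For the primary analysis the wording is "The model will include treatment, OAM use, visit, treatment-by-visit interaction as fixed effects, and baseline HbA1c as a covariate". For the <7.0% target it is "The model will include independent variables of treatment, OAM usage, visit, and treatment-by-visit interaction as fixed effects", with baseline HbA1c again a covariate. For weight and FSG it is "The MMRM model will include treatment, OAM usage, visit, baseline HbA1c strata". Every model in the table includes OAM usage.

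The SAP does not say how the baseline stratum is derived. That it comes from Visit 3 follows from the definition of baseline. The rationale in the protocol's amendment summary confirms this intention but gives no statistical reason for it.

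**The concern.** Stratified randomisation makes the arms more alike on the stratifying factor than chance would. An analysis that ignores a prognostic stratifying factor then reports a standard error that is too large. The usual default is therefore to put the factor used at randomisation into the model, and a departure calls for a reason.

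Here one of the two factors is carried through everywhere (OAM usage). The other is either replaced by a similar variable measured about three weeks later or represented only by continuous Visit 3 HbA1c. Patients near 8.5% can be randomised in one stratum and analysed in the other. Weight and FSG are the most exposed: SAP 5.3 puts both under type I error control, and their models have neither the randomised stratum nor continuous HbA1c.

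**Working it through.** **1. The plan's own figure.** The inputs in SAP 5.1 are "with 90% power assuming a treatment difference of 0.5% in HbA1c reduction", "standard deviation (SD)=1.2"% and "dropout rate of 15%, and 2-sided alpha of 0.05".

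- n per arm = 2(1.960 + 1.282)² × 1.2² / 0.5² = 121.05, so 122. With the t distribution, power is 89.997% at 122 and 90.2% at 123, so 123.
- 123 / 0.85 = 144.7, so 145 per arm and 290 in total. 290 / 0.6 = 483 screened.

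The sample size reproduces and does not depend on this point.

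**2. How many patients change stratum.** The documents give no HbA1c variability, so these inputs are assumed: between-patient SD 0.9%, mean 8.5%, Visit 1 values limited to the eligible 7.0% to 11.0%. The correlation between visits is ρ = 0.81 / (0.81 + w²), where w is the within-patient SD. For a cut at the median of a bivariate normal, the discordant share is arccos(ρ)/π. The simulation adds the eligibility limits.

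| w | ρ | arccos(ρ)/π | Simulated |
|---|---|---|---|
| 0.1 | 0.988 | 5.0% | about 5% |
| 0.2 | 0.953 | 9.8% | 10.4% |
| 0.3 | 0.900 | 14.4% | 15.3% |
| 0.4 | 0.835 | 18.5% | 19.9% |

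Of 290 patients, 10.4% is about 30 and 19.9% about 58.

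**3. Effect on the test.** The simulation used 246 completers, blocks of 4 within Visit 1 stratum, 4,000 runs per scenario and a single-time-point ANCOVA in place of the MMRM. Assumed inputs were Visit 1 HbA1c mean 8.5 and SD 1.0 limited to 7 to 11, visit correlation 0.80 or 0.95, slope of change on HbA1c −0.4 or −0.7, total SD 1.2, and effect 0 or 0.5. The Monte Carlo error of a 5% rate is about 0.0034.

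| HbA1c term in the model | Type I error | Power |
|---|---|---|
| None | 0.039–0.048 | 90.3–91.9% |
| Visit 3 stratum | 0.052–0.056 | 90.9–94.5% |
| Visit 1 stratum | 0.051–0.055 | 91.1–94.6% |
| Continuous Visit 3 (as in the primary model) | 0.050–0.053 | 91.4–96.5% |
| Continuous Visit 3 + Visit 1 stratum | 0.052–0.054 | 91.6–96.5% |

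- The first row shows the theoretical problem: with no HbA1c term, the test is conservative. None of the models tabulated above is in that position.
- Scenario by scenario, the two strata differ in power by at most 0.5 points, in both directions.
- Adding the Visit 1 stratum to the primary model's terms moves power by at most 0.2 points.

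**4. Where precision is available.** A second simulation took a generic continuous outcome with SD 1, 246 patients, w = 0.3, and correlation 0.3 or 0.6 with true HbA1c (3,000 runs each).

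| Correlation | SE, Visit 3 stratum | SE, Visit 1 stratum | SE, Visit 1 stratum + continuous HbA1c | Reduction from Visit 1 stratum alone |
|---|---|---|---|---|
| 0.3 | 0.1236 | 0.1234 | 0.1222 | 1 − 0.1222/0.1234 = 1.0% |
| 0.6 | 0.1111 | 0.1110 | 0.1045 | 1 − 0.1045/0.1110 = 5.9% |

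A parallel run under similar assumptions reached about 7%. Swapping one stratum for the other changes almost nothing; the continuous term supplies the gain. The weight and FSG models also adjust for the outcome's own baseline, which was not simulated. The correlation should therefore be read as what remains after that adjustment, so the gain may sit at the lower end.

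**The case against.** The strongest case against is that nothing is harmed. The primary and responder models do adjust for HbA1c, using a later value of the same analyte. Using the Visit 3 value is a defensible, openly prespecified choice that aligns the models with the study baseline. The reclassified share rests on assumed variability, and reclassification is not itself harm. Replacing one 8.5% dichotomy by another, older one gains nothing, and in the primary model it adds a dichotomy beside a continuous covariate that already carries the information.

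Most of this stands. Two stronger readings should be set aside:

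- A reader might infer that the primary model leaves HbA1c unadjusted, or that its type I error or power is compromised. The text of SAP 5.6 rules out the former, and the simulation does not support the latter.
- A reader might infer that changing the stratum would sharpen the weight and FSG comparisons. It would not; only the continuous term does.

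What remains is that the plan departs from analysing by the factor used at randomisation, states no statistical reason for doing so, and can correct this at almost no cost. The logistic, Cox and count models were not simulated, so neither harm nor its absence has been shown for them.

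**Conclusion.** The mismatch is real and follows from the current text: the HbA1c stratum used to randomise appears in no efficacy model. It is a minor point. For continuous endpoints the effect on type I error and power is negligible under every scenario tried, and the primary conclusion is not at risk.

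The 10% to 20% reclassification figure holds for within-patient SDs of 0.2% to 0.4% and falls to about 5% at 0.1%. The only material gain is a standard error about 1% to 7% smaller for weight and FSG. It comes from continuous baseline HbA1c and depends on how strongly those outcomes track HbA1c. The simulations used a single time point rather than the full MMRM.

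**What to change.** 1. Wherever a model carries an HbA1c stratum, specify the Visit 1 stratum recorded in the interactive web response system (IWRS). The exception is the prespecified baseline-HbA1c subgroup in SAP 5.12, which should be labelled as a Visit 3 grouping. That section's rule on subgroups that are stratification variables currently blurs the two.
2. Add continuous baseline HbA1c to the weight and FSG models (SAP 5.7.2 and the corresponding analyses in 5.10).
3. Add the IWRS stratum to the primary MMRM, the <7.0% model and the rescue Cox model, keeping continuous baseline HbA1c. Do this at least as a sensitivity analysis. If the main models stay as they are, give the reason in one sentence.
4. Align protocol 10.3.3.1, 10.3.3.2, 10.3.4.3 and 10.3.4.4. At present protocol 10.3.1 gives the key secondary continuous model without a stratum while 10.3.3.2 includes one. Protocol 10.3.3.2 also gives self-monitored glucose and insulin dose the primary-model terms, whereas SAP 5.8.2 and 5.8.3 use a stratum.

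**Cost:** wording in both documents and at most one or two degrees of freedom per model, with no change to the 290 patients. Changing the main primary model needs a documented justification, or a protocol amendment if it is judged a principal feature under protocol 10.3.1. The sensitivity-analysis route leaves that model unchanged.

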5.8. Additional Secondary Efficacy Analysis

5.8.1. Percentage of Patients Achieving a Target HbA1c $\leq 6.5\%$ and the Composite Outcomes

The single endpoint (HbA1c of $\leq 6.5\%$ at Week 28) will be analyzed using the same model described above for the analysis of patients achieving the target of 7%; double endpoint (HbA1c $< 7\%$ at Week 28, and without documented symptomatic hypoglycemia [$< 3.0 \text{ mmol/L}$] during the maintenance period [Weeks 12-28]); double endpoint (HbA1c $< 7\%$ at Week 28, and without

weight gain [<0.1 kg] at Week 28); and triple endpoint (HbA1c $<7\%$ at Week 28 and with no weight gain [<0.1 kg] at Week 28 and without documented symptomatic hypoglycemia [BG <3.0 mmol/L] during the maintenance period [Weeks 12-28],) will be analyzed by logistic regression. The model will include **baseline HbA1c**, OAM usage, and treatment as factors.

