5.9.2. Other Composite Outcomes

The other objectives include triple endpoint (HbA1c $< 7\%$ and no weight gain [$< 0.1\text{ kg}$] at Week 28, and no documented symptomatic hypoglycemia [BG $< 3.9\text{ mmol/L}$] during the maintenance

period); double endpoint (HbA1c <7% at Week 28 and no documented symptomatic hypoglycemia [BG < 3.9 mmol/L] during the maintenance period), and double endpoint (HbA1c <7% and with no weight gain [<0.1 kg] at Week 28) will be analyzed by the same model as that in Section [5.8.15.7.1](#).

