5.10. Efficacy Analysis without Censoring Post-Rescue or Early-Discontinuation Data

We will conduct some additional efficacy analysis without censoring the data after rescue therapy or premature treatment discontinuation (whichever occurs first). Missing endpoints will be imputed by jumping to the reference (J2R) method as described in Carpenter et al. 13, which assumed that the drug effect for missing data in both the placebo arm and dulaglutide arm was like the observed effect in the placebo arm. This approach in essence assumed that subjects would lose any treatment effect after the intercurrent events, which might be used as a worst-case scenario in terms of assuming patients with missing data received no drug benefit after the intercurrent events. Measurements include actual and change from baseline in HbA1c, body weight and FSG and frequency counts and percentage of patients achieving the target of HbA1c <7.0%. We will analyze HbA1c, body weight and FSG by ANCOVA model. For HbA1c, treatment and OAM usage are fixed effects and baseline is a covariate. For body weight and FSG, treatment, OAM usage, baseline HbA1c strata (<8.5%, and ≥8.5%) are fixed effects, and baseline dependent variable is a covariate. Percentages of patients achieving the target of HbA1c <7.0% will be analyzed using logistic regression with treatment and OAM usage as fixed effects and baseline HbA1c value as a covariate.

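### SAP 5.8.1 composites: no responder status after censoring, no uncensored analysis, and a severe hypoglycaemic event without a glucose value can still count as success

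*SAP*

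**What the plan says.** **Model.** SAP 5.8.1 defines two double endpoints and one triple endpoint. For these it says "during the maintenance period [Weeks 12-28],) will be analyzed by logistic regression", with baseline HbA1c, OAM usage and treatment as terms and no visit term. The HbA1c ≤6.5% endpoint in the same section instead follows the model of SAP 5.7.1: "The percentage of patients achieving the target of HbA1c <7.0% will be analyzed using longitudinal logistic regression with repeated measurements".

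**Population and censoring.** SAP 5.2 states "Both efficacy and safety analyses will be conducted using the intent-to-treat (ITT) population". It then states that "efficacy data from patients who started rescue therapy or premature treatment discontinuation (whichever occurs first) will be censored" from that point onwards. The missing-data statements in SAP 5.2 belong to the MMRM paragraph and give no rule for a binary endpoint.

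**Uncensored analysis.** SAP 5.10 restores data after rescue or drug stop and imputes missing endpoints by jump to reference. Its scope is: "Measurements include actual and change from baseline in HbA1c, body weight and FSG and frequency counts", plus the percentage reaching HbA1c <7.0%. No composite is listed.

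**Data available.** Protocol 5.1 keeps rescued patients in the trial through all visits. Protocol 8.1.1 does the same for patients who stop study drug, with planned efficacy and safety measurements still collected.

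**Hypoglycaemia component.** SAP 5.11.2 defines documented symptomatic hypoglycaemia as symptoms or signs together with a glucose below 3.0 (or 3.9) mmol/L. SAP Table 5.2 sets no glucose threshold for Level 3, and Protocol 9.2.2.1 accepts that a glucose value may be missing in such an event. SAP 5.11.2 also announces a Total hypoglycemia category (Levels 1 to 3) for use in 5.8.1 and 5.9.2, but no endpoint there names it.

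**Exploratory composites.** SAP 5.9.2 says these "will be analyzed by the same model as that in Section [5.8.15.7.1", a reference that does not resolve to one section.

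**The concern.** A patient rescued or taken off drug before Week 28 has no usable Week 28 HbA1c or weight under SAP 5.2, and so no defined composite outcome. An ordinary logistic regression omits records without an outcome. The result would then describe only patients who were neither rescued nor stopped early, even though the others were followed and measured.

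That loss is unlikely to be unrelated to outcome. Between Weeks 12 and 28, Protocol 7.7.5.3 triggers rescue at an average daily glucose above 11 mmol/L, which it equates to HbA1c 8.5%, far from the <7% target. How the treatment comparison shifts depends on how many patients are lost in each arm and how they would have scored.

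The second issue is one of meaning. These endpoints are meant to show control without hypoglycaemia. As defined, the most serious kind of event does not count against the patient if nobody recorded a glucose value.

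**Working it through.** **1. The plan's own figures.** SAP 5.1 gives a difference of 0.5, SD 1.2, two-sided alpha 0.05, 90% power and 15% dropout.
- n per arm = 2(1.960 + 1.282)² × 1.2² / 0.5² ≈ 2 × 10.51 × 1.44 / 0.25 ≈ 121.1, rounded up to 122. Noncentral-t power at 123 per arm is 0.902.
- 123 / 0.85 = 144.7, so 145 per arm and 290 in total. 290 / 0.60 = 483 screened.

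These reproduce, concern the primary endpoint only, and are untouched by this point. The documents give no planning rate for any composite and no rescue, drug-stop or Level 3 rate.

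**2. Four patients traced through the text.**
- *Rescued at Week 20, measured at Week 28.* Both measurements are censored, and responder status is undefined.
- *Qualifying event at Week 14, drug stopped at Week 16.* On observed data this patient has already failed the endpoints with a hypoglycaemia component. The SAP does not say whether the failure counts.
- *Drug stopped at Week 20, no event so far.* The Weeks 12-28 window is only partly observed, and no rule is given.
- *Level 3 event at Week 20 without a glucose value, on drug, HbA1c <7% and no weight gain at Week 28.* The definition in SAP 5.11.2 is not met, so the patient can count as a success on the triple endpoint and on the HbA1c-plus-hypoglycaemia endpoint. The HbA1c-plus-weight endpoint is unaffected.

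**3. Illustration of the unstated rule.** Assumed inputs:
- Success of 66.7% vs 33.3%, the HbA1c-only rates of the earlier trial quoted in Protocol 5.4. A composite would be lower, so 30% vs 15% is also shown.
- Loss around the planned 15% dropout, which is a stand-in and not a rescue or drug-stop rate.
- Lost patients all scored as failures: rate = p × (1 − loss).

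| Loss, dulaglutide / placebo | 66.7% vs 33.3% | Difference (OR) | 30% vs 15% | Difference (OR) |
|---|---|---|---|---|
| Complete-case | 66.7 vs 33.3 | 33.4 (4.01) | 30.0 vs 15.0 | 15.0 (2.43) |
| 15% / 15% | 56.7 vs 28.3 | 28.4 (3.32) | 25.5 vs 12.75 | 12.75 (2.34) |
| 10% / 20% | 60.0 vs 26.6 | 33.4 (4.14) | 27.0 vs 12.0 | 15.0 (2.71) |
| 20% / 10% | 53.4 vs 30.0 | 23.4 (2.67) | 24.0 vs 13.5 | 10.5 (2.02) |

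**4. Logical limits.** In whole patients with 22 lost per arm, complete-case is 82/123 vs 41/123.
- Lost dulaglutide patients all fail and lost placebo patients all succeed: (82 − 63)/145 = 13.1 points.
- The reverse: (104 − 41)/145 = 43.4 points.

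**5. Level 3.** One reclassified patient moves an arm's rate by 1/145 = 0.7 points.

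**The case against.** **Complete-case is nowhere stated.** Correct. It is the likely default of the named model, inferred because the SAP is silent.

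**The ITT commitment is not broken.** A reader might infer that SAP 5.2 promises a result for every randomised patient and that 5.8.1 breaks the promise. It does not: the same paragraph that names the ITT population goes on to censor efficacy data. What is missing is the rule for a patient so censored.

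**The model change is permitted.** Protocol 10.3.3.2 specified longitudinal logistic regression for these endpoints, and a reader might infer an undocumented departure. SAP 5.2 says "Any other change to the data analysis methods described in the protocol, and the justification for making the change, will be described" in the SAP and/or the clinical study report, so a missing reason in the SAP is not a defect. An event-free window also yields one outcome per patient for the hypoglycaemia composites.

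**The hypoglycaemia censoring was deliberate.** SAP 5.2 says "Safety analysis will not censor this part of data", while SAP 5.11.2 leaves out data after rescue or early drug stop. A reader might infer an unresolved conflict. The SAP revision history records removing those analyses, so the exclusion is a decision, and SAP 5.2 simply lacks the exception.

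**The scope of SAP 5.10 was chosen.** It matches Protocol 10.3.3.3, which was added after regulatory feedback, and other additional secondary endpoints are also absent. Adding the composites is therefore an improvement, not the correction of an error.

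**The Level 3 rule is consistent.** The same definition is used throughout, patients are told to record a glucose value during episodes, and recent severe hypoglycaemia is an exclusion. Such cases may be few. Level 3 events are also reported as SAEs and summarised under safety. This limits the size but does not change what the definition allows.

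**The cross-reference in SAP 5.9.2** looks like two section links run together and is clerical.

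**Conclusion.** The point holds at low severity. The text leaves a censored patient's composite status undefined, offers no uncensored composite analysis although the data are collected, and allows a Level 3 event without a glucose value to leave a patient a responder.

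The size cannot be determined from the documents. Under the assumptions above, the difference stays at 33.4 points or falls to as little as 23.4, and at the lower rates stays at 15.0 or falls to as little as 10.5. These are bounds that score every lost patient as a failure. A reader might take them as the expected bias or as the effect of the fix. They are neither, because the proposed analysis uses observed values and imputation.

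A reader might also infer from Protocol 10.3.3.2, which groups the composites under key secondary objectives, that type I error control is at stake. The objectives tables in both documents list them as additional secondary or exploratory, and the testing scheme in SAP 5.3 does not include them. The primary and key secondary conclusions are unaffected.

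**What to change.** **(a) Uncensored composites.** Add the composites to SAP 5.10 on the full ITT denominator.
- Use observed Week 28 HbA1c and weight after rescue or drug stop. Impute only what is truly missing, by jump to reference jointly for HbA1c and weight, and derive the composite in each imputed data set.
- Score any qualifying hypoglycaemic event observed in Weeks 12-28 as not achieved.
- State that time after last contact is treated as event-free. Add a sensitivity analysis that scores patients with an incomplete window as not achieved.
- Keep the current 5.8.1 fit, label it complete-case, and give it one stated rule for a partly observed window. The simplest consistent rule is that a patient censored before Week 28 is not evaluable. Adding back only the known failures would select on the outcome.

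**(b) Level 3.** Define the hypoglycaemia component as documented symptomatic hypoglycaemia below the threshold or any Level 3 event, in the SAP and in the matching protocol endpoint wording.

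**(c) Tidying.** Correct the cross-reference in SAP 5.9.2, add the hypoglycaemia exception to SAP 5.2, and assign Total hypoglycemia to an endpoint or delete it.

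**Cost.** SAP wording, a protocol wording edit for (b) and modest programming, with no new data. Reported response rates may be lower. In the illustration, if every lost patient is a failure, the dulaglutide rate falls by 0.667 × 0.15 = 10.0 points at 15% loss and by 0.667 × 0.20 = 13.3 points at 20% loss. The rule should be fixed before unblinding so that it cannot appear data-driven.
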